10.3.3 Sample size estimation for the primary safety analysis at 6 months

Primary safety analysis will be evaluated at 6 months and an estimation of 50 subjects results in 25 patient years at 6 months, which will yield enough safety data for the primary safety analysis. At the 12-month analysis 50 subjects results in 50 patient years.

10.3.4 Overall sample size considerations

In order to achieve 90% power both for the primary analysis (PTA4 and SNR, Investigational Device vs. Unaided) and the primary safety analysis, 50 evaluable subjects are needed. Each arm SSD and Conductive/Mixed should at least consist of 13 patients to assure a power of 90% in both arms for the primary analysis.

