4.2 Justification for the design of the clinical investigation

The design where the primary assessment consist of a comparison of the post-operative aided performance with the preoperative unaided performance is considered relevant for this purpose. The primary efficacy assessment of the investigation, i.e. threshold, free-field, pure tone average PTA4, is a relevant and objective method used by clinics internationally as a way to assess hearing performance. The test is not language specific (no words used), thus rendering comparative data in an international, multilingual setting.

The self-reported assessment of hearing outcome using the APHAB questionnaire was chosen as an important secondary efficacy assessment; hence, the APHAB scale was used for determination of the sample size in the investigation⁹. The APHAB has been used in investigations previously and has shown to be a good tool for measuring changes in patient benefits.

The rationale for measuring and collect data with Baha BP110 Power Sound Processor on a Softband as a secondary assessment is based on the fact that the FDA guideline for middle ear implants suggests that a comparative non-inferiority or superiority study design (using within-patient comparison) may be required.

The Baha BP110 Power Sound processor on a Softband was chosen for a secondary assessment, since the ATB System mimics the performance of a Baha Power Sound Processor (with the same 55 dB fitting range) on the passive transcutaneous Baha Attract System¹. Therefore it is also a relevant choice to present as a postoperative hearing situation for the subject.

This investigation is limited to adult subjects. The paediatric population constitutes an inhomogeneous patient group (age-related), and currently there are no audiological tests that are suitable for comparisons across age ranges and across multiple countries/languages.

The follow-up period of 12 weeks post-surgery, 8 weeks post fitting for the primary analysis is chosen as it is judged as long enough for the subjects to adapt and get used to the hearing performance with this investigational device. The total length of the investigation is judged long enough to collect hearing performance and safety data as long term data.

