10.3 Sample size calculation

10.3.1 Sample size calculation for the primary efficacy analysis

In order to achieve 90% power to detect a clinically significant difference of 10 dB in free-field hearing thresholds or 10 dB SNR between the unaided situation and the ATB System at the 3 months visit with Fisher's non-parametric permutation test for paired observations, one-sided test with significance level 0.025, on the ITT population 11 (PTA-4) and 13 (SNR) evaluable subjects are needed. The sample size was calculated using simulation on study id CBAS5675 (Cochlear 2017) data which used the simulated ATB system on Mixed/Conductive subjects. The within subject SD for change Unaided to ATB in PTA4 was 9.5 dB and 11.3 SNR. Since significant result want to be detected in both arms (SSD and Conductive/Mixed) 13+13=26 subjects should be included in the investigation.

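### Protocol 10.3.4 and SAP 1.5.3 claim 90% power for a primary safety analysis that has no hypothesis or test; an exposure-based number is mislabelled as powered

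*Protocol*

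**What the plan says.** The plan gives four accounts of the sample size.

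- **Primary efficacy (protocol 10.3.1, SAP 1.5.1).** The target is "90% power to detect a clinically significant difference of 10 dB in free-field hearing thresholds or 10 dB SNR", with a "one-sided test with significance level 0.025, on the ITT population 11 (PTA-4) and 13 (SNR) evaluable subjects are needed". Adding the two arms gives "13+13=26 subjects should be included in the investigation".
- **APHAB (protocol 10.3.2 only).** A 15-unit benefit with SD 23.3 needs 28 evaluable subjects in the pooled population, raised to 30 for two dropouts. The SAP has no APHAB sample size calculation.
- **Safety (protocol 10.3.3, SAP 1.5.2).** "50 subjects results in 25 patient years at 6 months", which is judged sufficient, and 50 patient-years at 12 months. These sections claim no power.
- **Overall (protocol 10.3.4, SAP 1.5.3).** To have 90% power for PTA4 and SNR "and the primary safety analysis, 50 evaluable subjects are needed". The protocol adds: "Each arm SSD and Conductive/Mixed should at least consist of 13 patients to assure a power of 90% in both arms".

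Protocol 4.2 says separately that "the APHAB scale was used for determination of the sample size in the investigation".

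On the safety analysis itself, protocol 10.2.3 lists variables, and 10.6 says that numbness, adverse events and device deficiencies will be presented. SAP 4.1 restricts those three to descriptive analysis, and SAP 4.11 provides for summaries.

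**The concern.** Power is the probability that a specified test rejects a specified null hypothesis under a specified alternative. Without a test there is nothing for 90% to refer to. Yet the overall sample size statement in both governing documents gives the safety analysis the same 90% as the two efficacy endpoints.

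This matters because the step from 30 subjects to 50 is made for safety. The section that justifies the step speaks only of exposure, with no criterion for how much is enough, and the summary then describes the result as power. Someone reading only 10.3.4 could take a clean 6-month result for a new active implant as coming from an adequately powered safety assessment.

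The sentence in 4.2 adds a second inconsistency. It names APHAB as what determined the sample size, whereas 10.3.4 does not mention APHAB and APHAB does not lead to 50.

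**Working it through.** **1. Reproduce the efficacy and APHAB figures.** The inputs come from protocol 10.3.1 and 10.3.2: one-sided alpha 0.025, power 90%, differences of 10, 10 and 15. For the SDs, "The within subject SD for change Unaided to ATB in PTA4 was 9.5 dB and 11.3 SNR"; APHAB has 23.3. The normal approximation is n = (SD × (1.960 + 1.282) / difference)². The t-test column uses the noncentral t distribution. The last column is a simulated sign-flip permutation test on normal data (3,000 simulations).

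| Endpoint | Normal formula | t test | Stated | Permutation power at stated n |
|---|---|---|---|---|
| PTA4 | (9.5 × 3.242 / 10)² = 9.5, so 10 | 12 | 11 | 87% |
| SNR | (11.3 × 3.242 / 10)² = 13.4, so 14 | 16 | 13 | 83% |
| APHAB | (23.3 × 3.242 / 15)² = 25.4, so 26 | 28 | 28 | 91% |

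APHAB reproduces exactly with the t test, and PTA4 falls between the two methods. The SNR figure of 13 is one below the normal formula and three below the t test. The sponsor simulated from earlier study data that are not in the documents, so 13 is not refuted here and is taken as stated.

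**2. Totals from the power calculations.** Primary endpoints: 13 + 13 = 26. APHAB: 28 + 2 = 30. Neither gives 50.

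**3. Reproduce the safety exposure.** 50 × 0.5 years = 25 patient-years, and 50 × 1 year = 50. Both are correct if nobody leaves early. Protocol 3.7 does not replace subjects lost after surgery, and 3.6 gives implant loss as an example of a reason for discontinuation, so these are upper values.

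**4. Try to reproduce the safety power.** The required inputs, and what the documents supply:

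- Hypothesis: none in protocol 10.2.3 or 10.6, or in SAP 4.11.
- Acceptance rate or margin: none.
- Alpha and test: none. The six-step confirmatory hierarchy in SAP 4.1 has no safety item.
- Bone-conduction audiogram: SAP 4.11.4 only presents it, with no group-level criterion.
- Change in numbness: SAP 4.11.1 leaves evaluation optional and names no test.

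The 90% cannot be computed.

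**5. What 50 subjects do provide.** Assume 50 independent subjects, all followed.

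- Risk at which at least one event is seen with 90% probability: 1 − 0.10^(1/50) = 4.5%.
- Upper limit with 0/50 events, one-sided 97.5%: 1 − 0.025^(1/50) = 7.1%.
- The same at one-sided 95%: 1 − 0.05^(1/50) = 5.8%.
- Zero events in 25 patient-years, one-sided 95%: −ln(0.05)/25 = 0.12 events per patient-year.
- Chance of seeing any event at a true risk of 1%: 1 − 0.99^50 = 39%.

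The 1% in the last line is only an illustration. It is the approximate implant loss rate that protocol 9.2.4 gives for the percutaneous Baha Connect System.

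**6. Efficacy at 50.** With an assumed even split of 25 per arm, t-test power is 99.9% for PTA4 and 98.9% for SNR. Pooled APHAB power at 50 is 99.4%.

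**The case against.** The strongest reply is that this is one loose sentence, carried into the SAP, and that nothing depends on it. Protocol 10.3.3 and SAP 1.5.2 give a genuine basis for 50, the patient-year arithmetic is right, and no safety success rule exists that could turn the phrase into a claim. Most of that stands, and it limits the point in several ways.

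- A reader might infer that the sample size has no valid basis, or that 50 is wrong or too small. The documents do not support this. Exposure is a stated basis separate from power, and 50 exceeds both 26 and 30. The fair criticism of 10.3.3 is that it gives no criterion for sufficient exposure.
- A reader might infer that the APHAB sentence in 4.2 is false and should be removed. It does not say that APHAB alone set the size, or that it set 50, and 10.3.2 does contain an APHAB calculation. It needs reconciling, not deleting.
- A reader might infer that no safety events are defined. They are: adverse events of special interest in protocol 7.2.3 and SAP 3.3.2, and in protocol 7.2.4 an individual threshold shift above 15 dB HL that is reported as an adverse event. What is missing is a group-level hypothesis, acceptance rate and test.
- The 1% benchmark is not matched to this device. Protocol 9.1 expects a lower risk of osseointegration failure than with Baha Connect, and 9.2.5 reports no confirmed implant loss from that cause with Baha Attract. The 39% should not be read as a prediction for this trial.

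The reply does not remove the defect. Both documents state a 90% operating characteristic for safety that the design does not have.

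**Conclusion.** The point holds as a mislabelling. The 90% power attached to the primary safety analysis in protocol 10.3.4 and SAP 1.5.3 is undefined, and 50 is an exposure-based number presented as a powered one. Protocol 4.2 is inconsistent with 10.3 on what determined the sample size.

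The gap is between a claimed 90% power and a descriptive analysis whose precision is an upper limit of 7.1% when no events occur. That limit is at one-sided 97.5%, the confidence level named in SAP 4.1, and it assumes complete follow-up of 50 independent subjects. With dropout it would be wider.

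No arithmetic in the safety section is wrong, no confirmatory conclusion is affected, and the number of subjects is not called into question. Whether 13 per arm really gives 90% power for SNR is a separate matter that this point does not settle.

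**What to change.** 1. In protocol 10.3.4 and SAP 1.5.3, limit the 90% power claim to PTA4 and SNR, with at least 13 subjects per arm, and remove the primary safety analysis from it.
2. In the same places, say that 50 was chosen for safety exposure: 25 patient-years at 6 months and 50 at 12 months, before dropout.
3. Replace the safety power claim with a precision statement such as: with 50 subjects there is a 90% probability of observing at least one event whose true risk is about 4.5%, and with 0/50 events the one-sided 97.5% upper limit is 7.1%. The 5.8% limit at one-sided 95% may be added if it is labelled as such.
4. In protocol 4.2, say that APHAB sized the secondary analysis (28 subjects, or 30 with dropout) and did not determine the overall 50.

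The cost is a wording amendment to the two documents. The stated safety property becomes less favourable. The number of subjects, the data collected and the analyses stay as they are.

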10.5 Efficacy analysis

10.5.1 Primary efficacy analysis

Primary efficacy analysis will be determined by analysis of change in free-field threshold audiometry: PTA4 (mean of 500, 1000, 2000 and 4000Hz) and change adaptive speech recognition in noise (50% performance), from preoperative Unaided versus Investigational device at the 3 months visit for the ITT population, using Fisher's one-sided non-parametric permutation test for paired observations at a significance level of 0.025 to demonstrate an improvement in PTA4. Each arm SSD and Conductive/Mixed will be tested separately. Both PTA4 and SIQ must be significant at alpha 0.025 for the primary analysis to be considered as confirmative in each arm separately. In addition, a pooled analysis for all subjects will be made.

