1.5.3 Overall sample size considerations

In order to achieve 90% power both for the primary analysis (PTA4 and SNR, Investigational Device vs. unaided) and the primary safety analysis, 50 evaluable subjects are needed. Each arm SSD and Conductive/Mixed should at least consist of 13 patients to assure a power of 90% in both arms for the primary analyses.

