4 STATISTICAL METHODOLOGY

4.1 General Methodology

Since all included subjects will have measurements of the primary and important secondary efficacy variables for unaided hearing, with the Investigational device and with a Baha power sound processor on a Baha Softband, all statistical analyses will be paired. All statistical analyses will be non-parametric. In order to choose the most powerful test, the Fisher's non-parametric permutation test for paired observations will be used for all paired analyses of continuous variables. The permutation tests use the measured values and not only the ranks in the calculations. For paired analysis of dichotomous and ordered categorical variables the Sign test will be used.

The analyses will be performed in the following priority:

1. Investigational Device vs. Unaided
2. Investigational Device vs. Baha power sound processor on a Baha Softband

In addition to the change variables the distribution of all efficacy variables will be presented by visit, where applicable.

The main efficacy analysis will be performed on the ITT population and complementary efficacy analyses will be performed on the PP population. The main analysis will be performed after the 3 month visit. A complementary analysis will be performed 9 months after the main analysis (12-month visit). All significance tests will be one-sided and performed at the 2.5% significance level to demonstrate an improvement with Investigational Device.

The hierarchical testing procedure below is introduced to guarantee that the probability of Type I error is < 2.5% for all confirmative statements. The order of the hierarchical testing procedure will be:

1. PTA 4 pre-operative unaided vs 3 months (Primary efficacy analysis)
2. Adaptive speech recognition in noise (50% performance), speech to noise ratio (SNR) pre-operative unaided vs 3 months
3. Speech in quiet at 65dB SPL pre-operative unaided vs 3 months
4. APHAB Global pre-operative unaided vs 3 months aided
5. Hearing attribute (HUI-III) pre-operative unaided vs 3 months
6. Mean of the 12 items in the SSQ pre-op unaided vs 3 months

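### The minimum of 13 per arm is the sample size for SNR alone; the primary rule needs PTA4 and SNR both significant, and no joint power supports the stated 90%

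*Protocol*

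**What the plan says.** Protocol 10.3.1 (repeated in SAP 1.5.1) aims at 90% power for a difference of 10 on each endpoint, one-sided 0.025, with the paired permutation test, and concludes that "on the ITT population 11 (PTA-4) and 13 (SNR) evaluable subjects are needed". On the source it says: "The sample size was calculated using simulation on study id CBAS5675 (Cochlear 2017) data which used the simulated ATB system on Mixed/Conductive subjects". On variability: "The within subject SD for change Unaided to ATB in PTA4 was 9.5 dB and 11.3 SNR". The larger size is then taken for each arm, 13 + 13 = 26.

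Protocol 10.3.4 says each arm "should at least consist of 13 patients to assure a power of 90% in both arms for the primary analysis", and SAP 1.5.3 says the same: "should at least consist of 13 patients to assure a power of 90% in both arms for the primary analyses". Both sections define the primary analysis as PTA4 and SNR. The same paragraph extends the 90% to safety: "and the primary safety analysis, 50 evaluable subjects are needed".

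The success rule is in Protocol 10.5.1 and, identically, SAP 4.10.1: "Both PTA4 and SIQ must be significant at alpha 0.025 for the primary analysis to be considered as confirmative in each arm separately". SIQ appears in neither abbreviation list. Protocol 10.2.1 and 10.3.4 and SAP 3.2.1 all pair PTA4 with speech in noise, so SIQ is read here as the SNR. SAP 4.1 gives a fixed testing order per arm whose first step is labelled "PTA 4 pre-operative unaided vs 3 months (Primary efficacy analysis"), with SNR second.

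**The concern.** Power to win on both endpoints cannot exceed power on the weaker one. It equals that power only if every trial that succeeds on SNR also succeeds on PTA4. Taking the larger of two single-endpoint sizes therefore gives at most 90% for the pair, and normally less. Assurance of 90% is claimed for a rule that was never sized.

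The minimum matters because it is the only stated safeguard for the smaller arm. The documents give no expected mix of SSD and Conductive/Mixed subjects, so a 13:37 split of the 50 would comply. The 13 has no allowance for dropout, and subjects lost after surgery are not replaced (Protocol 3.7). The SDs come from Mixed/Conductive subjects only, yet they also set the SSD minimum.

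If an arm ends near 13 and misses on one endpoint, a reader told that 90% was assured could take chance for lack of benefit.

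**Working it through.** **Inputs** (Protocol 10.3.1, SAP 1.5.1): difference 10 on each endpoint; SD of the paired change 9.5 (PTA4) and 11.3 (SNR); one-sided alpha 0.025. The rule is both endpoints significant, per arm.

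**1. The plan's own figures.** Normal approximation, n = ((1.960 + 1.2816) × SD / 10)²:
- PTA4: (3.2415 × 0.95)² = 9.5, so 10 (stated 11).
- SNR: (3.2415 × 1.13)² = 13.4, so 14 (stated 13).

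The noncentral t gives 12 and 16. The stated sizes are thus close to the normal approximation, but 13 for SNR is short of the t result. The sponsor's simulation used pilot data that are not in the documents, so it cannot be rerun.

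**2. Each endpoint alone at n = 13.** Noncentrality is √13 × 10 / SD, which is 3.80 for PTA4 and 3.19 for SNR, on 12 degrees of freedom.
- Noncentral t: PTA4 0.9355, SNR 0.8334.
- Normal approximation: PTA4 0.967, SNR 0.891.
- Simulated sign-flip permutation test with normal changes: about 0.94 and 0.83, in line with the t.

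**3. Both endpoints at n = 13, normal changes.**
- Independent: 0.9355 × 0.8334 = 0.780.
- Correlation 0.5: 0.802. Correlation 0.8: 0.820.
- Fully dependent: 0.833.
- Permutation simulation over the same correlations: 0.777 to 0.835.

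Splitting the gap to 90%: 90 − 83.3 = 6.7 points come from SNR alone under normal changes. Up to 5.4 points (0.8334 − 0.7796) come from requiring both endpoints.

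**4. Both endpoints at n = 13, accepting the sponsor's 90% for SNR.** 0.90 × 0.9355 = 0.842 if independent, and at most 0.90 if fully dependent.

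**5. Sensitivity to the shape of the changes** (permutation simulation; joint power at correlation 0 / 0.7; shapes are assumptions):

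| Shape of changes | n = 13 | n = 17 | n = 25 |
|---|---|---|---|
| Normal | 0.786 / 0.811 | 0.923 / 0.920 | 0.991 / 0.988 |
| Right skew, gamma shape 8 (SNR alone 0.90) | 0.876 / 0.888 | 0.967 / 0.964 | – |
| Right skew, gamma shape 4 | 0.917 / 0.916 | – | – |
| Left skew, gamma shape 8 | 0.706 / 0.757 | 0.866 / 0.878 | – |
| Left skew, gamma shape 4 | 0.694 / 0.745 | 0.851 / 0.854 | 0.967 / 0.963 |

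**6. Larger arms, noncentral t, normal changes.** Joint power is 0.912–0.928 at 17 and 0.988–0.989 at 25.

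**7. Borrowed SD in the SSD arm** (assumed range 10.3 to 13 for SNR). SNR power at 13 runs from 0.894 down to 0.721. With normal changes, 90% for SNR at 13 would need an SD of 10.2, against the stated 11.3.

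**8. Safety.** Protocol 10.3.3 offers only patient-years, and SAP 4.1 limits adverse events, numbness and device deficiencies to description. With no test there is no power. The precision available with no events in 50 subjects is a one-sided 97.5% upper bound of 1 − 0.025^(1/50) = 7.1%.

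**The case against.** The sponsor sized the trial by simulation on real data whose shape and PTA4–SNR correlation are not shown, and the range found here at 13 (69% to 92%) contains 90%. The 84% also mixes two models: a simulated 90% for SNR and a normal-theory 93.55% for PTA4. If PTA4 is instead calibrated to the sponsor's own 90% at 11, its power at 13 is 0.948 and the independent case becomes 0.90 × 0.948 = 85.3%. Where one skewed distribution is used for both endpoints and gives 90% for SNR, joint power is 88–89%, a shortfall of only one to two points. Most of the gap in the 78–83% range comes from assuming normality. With 50 subjects planned, only an arm that ends near the minimum is affected. On the SAP 4.1 order, PTA4 could be confirmative alone, and 13 then gives 93.6%.

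Much of this stands. It limits the size of the problem and rules out saying that the 90% is false. It does not supply a basis for the claim, because the simulation is reported per endpoint and SAP 4.10.1 keeps the both-endpoints rule alongside the SAP 4.1 order. If SIQ meant speech in quiet, the second required endpoint would have no power calculation at all. Nothing in the objection rescues a power figure for the safety analysis.

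**Conclusion.** The concern holds. The 90% stated for 13 per arm belongs to SNR alone and is unsupported for the rule that decides success. Accepting the sponsor's SNR figure, a device with exactly the assumed effect would miss the joint rule in about 10–16% of cases in an arm of 13. With normal changes it would miss in 17–22%. A design with true 90% power misses 10%, so the excess is 0–6 and 7–12 points respectively.

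These figures assume a difference of 10 on both endpoints, the stated SDs, non-negative correlation and SIQ read as SNR. Negative correlation would lower the 84% only to 83.5%. The SSD arm carries further uncertainty because its SDs are borrowed. With arms near 25 the efficacy concern disappears, so the total sample size is not in question. The 90% power for the safety analysis has no meaning as written.

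**What to change.** - **Protocol 10.3.4 and SAP 1.5.3:** replace the assurance of 90% with joint PTA4-and-SNR power per arm and its distributional basis. Use either the joint figure from the pilot-data simulation, or normal changes: about 78–83% at 13, 91–93% at 17 and 99% at 25.
- **Protocol 10.3.1 and SAP 1.5.1:** say that 13 is the SNR size alone and that the SSD arm uses SDs from Mixed/Conductive subjects.
- **Same edit:** replace SIQ with the intended endpoint in Protocol 10.5.1 and SAP 4.10.1, and reconcile the both-endpoints rule with the SAP 4.1 order and its label for PTA4.
- **Safety:** remove the 90% power and state precision (0 of 50 events, one-sided 97.5% upper bound 7.1%).
- **Optional:** report power for the per-arm APHAB step in SAP 4.1. With Protocol 10.3.2's difference of 15 and SD of 23.3 it is about 57% at 13 and 87% at 25, because the 28 there was sized for the pooled test.

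The cost is text changes plus one rerun of the existing simulation that counts a success only when both endpoints are significant. No extra patients or new enrolment rule are needed.
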